1.6 Rationale for Dose Selection

1.6.1 Rationale for Birinapant Starting Dose

The starting dose for the first in human study of birinapant (birinapant Investigator's Brochure) was 0.18 mg/m² and doses were escalated to 63 mg/m². Two patients out of three (67%) who received birinapant at 63 mg/m² developed Grade 2 AEs of Bell's palsy. Based upon these events the dose of 63 mg/m² of birinapant was considered to be above the maximum tolerated dose (MTD). The MTD of birinapant was defined at a dose of 47 mg/m² administered once weekly. Further clinical studies have utilized total weekly doses of birinapant up to and including 22 mg/m² weekly in combination with chemotherapy. The starting dose escalation cohort of 5.6 mg/m² weekly is consistent with these data, and is below the combination MTD seen previously in the birinapant program when used in combination with other cancer drugs.

1.6.2 Rationale for Pembrolizumab Dose Selection

The dose of pembrolizumab planned to be studied in this trial is 200 mg Q3W. The dose approved in the United States and several other countries is 2 mg/kg every 3 weeks (Q3W). Information on the rationale for selecting 200 mg Q3W is summarized below.

In KEYNOTE-001, an open-label Phase 1 study conducted to evaluate the safety, tolerability, pharmacokinetics (PK) and pharmacodynamics, and anti-tumor activity of pembrolizumab when administered as monotherapy. The dose escalation portion of this trial evaluated three dose levels, 1 mg/kg, 3 mg/kg and 10 mg/kg, administered every 2 weeks (Q2W) and dose expansion cohorts evaluated 2 mg/kg Q3W and 10 mg/kg Q3W in subjects with advanced solid tumors. All dose levels were well tolerated and no dose-limiting toxicities were observed. This first-in-human study of pembrolizumab showed evidence of target engagement and objective evidence of tumor size reduction at all dose levels. No MTD has been identified. In addition, two randomized cohort evaluations of melanoma subjects receiving pembrolizumab at a dose of 2 mg/kg versus 10 mg/kg Q3W have been completed,

and one randomized cohort evaluating 10 mg/kg Q3W versus 10 mg/kg Q2W has also been completed. The clinical efficacy and safety data demonstrate a lack of important differences in efficacy or safety profile across doses.

An integrated body of evidence suggests that 200 mg Q3W is expected to provide similar response to 2 mg/kg Q3W, 10 mg/kg Q3W and 10 mg/kg Q2W. Previously, a flat pembrolizumab exposure-response relationship for efficacy and safety has been found in subjects with melanoma in the range of doses between 2 mg/kg and 10 mg/kg. Exposures for 200 mg Q3W are expected to lie within this range and will be close to those obtained with 2 mg/kg Q3W dose.

A population pharmacokinetic (PK) model, which characterized the influence of body weight and other patient covariates on exposure, has been developed. The PK profile of pembrolizumab is consistent with that of other humanized monoclonal antibodies, which typically have a low clearance and a limited volume of distribution. The distribution of exposures from the 200 mg fixed dose is predicted to considerably overlap those obtained with the 2 mg/kg dose and importantly will maintain individual patient exposures within the exposure range established in melanoma as associated with maximal clinical response. Pharmacokinetic properties of pembrolizumab, and specifically the weight-dependency in clearance and volume of distribution are consistent with no meaningful advantage to weight-based dosing relative to fixed dosing.

In translating to other tumor indications, similarly flat exposure-response relationships for efficacy and safety as observed in subjects with melanoma can be expected, as the anti-tumor effect of pembrolizumab is driven through immune system activation rather than through a direct interaction with tumor cells, rendering it independent of the specific tumor type. In addition, available PK results in subjects with melanoma, NSCLC, and other tumor types support a lack of meaningful difference in pharmacokinetic exposures obtained at tested doses among tumor types. Thus the 200 mg Q3W fixed-dose regimen is considered an appropriate fixed dose for other tumor indications as well.

A fixed dose regimen will simplify the dosing regimen to be more convenient for physicians and to reduce potential for dosing errors. A fixed dosing scheme will also reduce complexity in the logistical chain at treatment facilities and reduce wastage. The existing data suggest 200 mg Q3W as the appropriate dose for pembrolizumab.

2 STUDY OBJECTIVES

2.1 Study Objectives Dose Escalation Phase

2.1.1 *Primary Objective*

To determine the safety and tolerability of the recommended phase 2 dose (RP2D) of birinapant when given in combination with pembrolizumab IV

2.1.2 Secondary Objective

To assess preliminary efficacy of the combination of pembrolizumab and birinapant in patients with relapsed or refractory cancer by effects on tumor size as measured by imaging (CT or MRI) assessed by RECIST 1.1.

2.1.3 Exploratory Objectives

1. To assess preliminary efficacy of the combination of pembrolizumab and birinapant in patients with relapsed or refractory cancer by effects on tumor size as measured by imaging (CT or MRI) assessed by iRECIST.
2. To determine the pharmacodynamic markers of birinapant and of pembrolizumab when given in combination at the schedule and dose as defined by the protocol, to include but not to be limited to mechanism of action (inhibition of cIAP1), and of immune surveillance and activation.
3. To assess biomarkers that might predict for responders to the combination treatment and allow comparison to known potential predictive biomarkers of pembrolizumab response.
4. To evaluate birinapant pharmacokinetics in plasma when administered in combination with pembrolizumab.

2.2 Study Objectives Dose Expansion Phase

2.2.1 Primary Objective

The primary objective in each of the cohorts is as follows:

1. To determine whether the combination of pembrolizumab and birinapant has sufficient antitumor activity, as assessed by ORR, against colorectal cancer to warrant more extensive development.
2. To determine whether the combination of pembrolizumab and birinapant has sufficient antitumor activity, as assessed by ORR, against ovarian cancer to warrant more extensive development.
3. To determine whether the combination of pembrolizumab and birinapant has sufficient antitumor activity, as assessed by ORR, against cervical cancer to warrant more extensive development.
4. To determine the safety and tolerability of the RP2D of birinapant when given in combination with pembrolizumab to patients in the various solid tumors cohort

2.2.2 Secondary Objectives

1. To assess the safety and tolerability of the combination of pembrolizumab and birinapant; Overall and in the defined tumor types, colorectal cancer, ovarian cancer and cervical cancer.

2. To assess clinical activity of the combination of pembrolizumab and birinapant in the defined tumor types by effects on tumor response, including CBR, time to response and duration of response, assessed by RECIST 1.1
3. To assess clinical activity of the combination of pembrolizumab and birinapant in the defined tumor types by effect on overall survival
4. To assess clinical activity of the combination of pembrolizumab and birinapant in the defined tumor types by effect on progression free survival.

2.2.3 Exploratory Objectives

1. To assess clinical activity of the combination of pembrolizumab and birinapant in the defined tumor types by effects on tumor response, including: CBR, time to response, duration of response, iBOR, duration of iBOR and time to iCPD, assessed by iRECIST
2. To assess the pharmacodynamic markers of birinapant and of pembrolizumab when given in combination at the schedule and dose as defined by the protocol, to include but not to be limited to mechanism of action (inhibition of cIAP1), and of immune surveillance and activation.
3. To determine biomarkers that might predict for response and/or indicate response to the combination treatment and allow comparison to known potential predictive biomarkers of pembrolizumab response.
4. To evaluate birinapant pharmacokinetics in plasma when administered in combination with pembrolizumab

3 INVESTIGATIONAL PLAN

3.1 Description of Study Design

This is a phase 1/2, multicenter, single-arm, open-label, dose-escalation, safety, tolerability, pharmacokinetic and pharmacodynamic study of birinapant and pembrolizumab, conducted in male and female patients, ≥ 18 years of age, who have relapsed or refractory solid tumors. Patients must qualify for study participation within 28 days before initiation of study-drug treatment; must have a histologically confirmed solid malignancy that is metastatic or unresectable and for which standard curative or palliative measures do not exist or are no longer effective; must have measurable disease according to RECIST v 1.1 and must have an Eastern Cooperative Oncology Group (ECOG) score of 0 or 1.

3.1.1 Description of Study Design Dose Escalation Phase

The dose escalation phase of this study will employ a sequential group dose-escalation design to determine the dose-limiting toxicity (DLT) and RP2D of birinapant administered in combination with pembrolizumab, both administered as a 30-minute intravenous (IV) infusion. Pembrolizumab will be administered first on Day 1. The birinapant infusion will begin 30 minutes (+10 minutes) following the completion of the pembrolizumab infusion on

Day 1. An additional dose of birinapant only will be administered on Day 8. The dose levels of birinapant and pembrolizumab are outlined in [Table 2](#).

Table 2 Dose Escalation Schedule

Dose-Escalation Schedule	
Dose Level	Pembrolizumab + Birinapant (per 21-day cycle)*
Level -1	200 mg pembrolizumab on Day 1 + birinapant 2.8 mg/m²/week on Days 1 and 8
Level 1	200 mg pembrolizumab on Day 1 + birinapant 5.6 mg/m²/week on Days 1 and 8
Level 2	200 mg pembrolizumab on Day 1 + birinapant 11 mg/m²/week on Days 1 and 8
Level 3	200 mg pembrolizumab on Day 1 + birinapant 17 mg/m²/week on Days 1 and 8
Level 4	200 mg pembrolizumab on Day 1 + birinapant 22 mg/m²/week on Days 1 and 8

*Note: A week without treatment (i.e., Days 15-21) will follow the second week of treatment, immediately after which the next 21-day cycle commences.

A minimum of 3 and up to 6 evaluable patients will be enrolled per dose level. For patients enrolled in Dose Level 1, the birinapant starting dose will be 5.6 mg/m²/week. Dose escalation of birinapant will occur in up to three steps. The Safety Review Committee (SRC) will review all the cumulative safety data up to and including completion of Day 21 for the last patient in a cohort from that treatment group prior to dose escalation. Upon review of the safety data the SRC will determine whether or not the safety data supports dose escalation to the next sequential dose level. If the first dose level (5.6 mg/m²) is deemed intolerable, defined as ≥ 2 patients from 3-6 experiencing a DLT, the SRC may decrease the starting dose of the next dosing cohort to 2.8 mg/m² (dose level -1).

If 1 of the 3 to 6 patients enrolled at a given dose level experiences a DLT, enrollment at the next dose level will proceed, if the next highest dose has not already been declared intolerable. However, if 1 of these 3 to 6 patients experiences a DLT at the given dose level and the next highest dose has already been declared intolerable, a minimum of 6 patients are to be enrolled at the given level and the dose at the given level may be the RP2D. A separate safety review will be performed by the SRC to determine the RP2D of the combination of birinapant and pembrolizumab and to begin the dose-expansion phase of the study.

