3.1.3 Safety Review Committee Dose Escalation Phase

A SRC will be involved in the conduct of the dose escalation phase of this study. The SRC will be comprised of representatives from the Sponsor and the study sites, and the SRC may recommend that the study be interrupted or terminated at any time if, in their judgment, serious or unexpected AEs of sufficient concern warrant such action. See reporting requirements ([Section 8.3](#)) for Serious AEs (SAEs). The SRC has the responsibility for monitoring the clinical study's progress and the safety of the participating patients

Following completion of a dosing level, an evaluation of the safety of that dose will be performed by the SRC (based on cumulative data to the time of SRC assessment). The SRC will review the safety, efficacy and pharmacodynamic data (when available) from all patients enrolled at each dose level to confirm any DLTs that were experienced and to make a recommendation regarding enrollment in the next dose level. Each of the 3 to 6 patients at a dose level must have completed Cycle 1 (21-day cycle) to be eligible for SRC review. On the basis of the findings, the committee will have several options:

1. Recommend escalation to the next dose level,
2. In case of unexpected or unacceptable toxicity during the dose escalation phase recommend early discontinuation of the study, or
Alter the subsequent dose as per the dose escalation criteria presented in [Section 5.4](#).

The SRC will make the decision on RP2D based on an MTD of the combination being the occurrence of greater than 2 defined grade 3 or above SAEs (for definition of DLTs see section 5.4) in the final cohort of 3 plus 3 subjects. In the absence of an MTD, the SRC will consider pharmacodynamic and PK of birinapant as applicable considering that birinapant monotherapy has been studied previously at 10 to 63 mg/m². Doses > 47 mg/m² will not be considered.

Further details on the SRC procedures are presented in the SRC-charter

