5.4 Dose-Limiting Toxicity and Recommended Phase 2 Dose

The inter-patient dose escalation of birinapant will be based on the number of patients that experience a DLT. A DLT is a clinically significant event attributed to birinapant, pembrolizumab, or the combination of the 2 study drugs, during the first cycle of drug therapy and is defined as follows:

Non-hematological toxicity:

- Common Toxicity Criteria for Adverse Event (CTCAE; 4.03) Grade 3 nausea, vomiting, or diarrhea despite maximal (according to treating investigator) anti-emetic or anti-diarrheal treatment and lasting > 48 hours; or Grade 4 vomiting or diarrhea;
- \geq Grade 3 other non-hematological toxicity, excluding isolated laboratory abnormalities without clinical sequelae, except for the following:
 - Prolonged (> 7 days) serum amylase or lipase elevation;
 - Prolonged (> 7 days) aspartate aminotransferase (AST) elevation;
 - Prolonged (> 7 days) alanine aminotransferase (ALT) elevation;All of which will be considered dose limiting.

Hematological toxicity:

- Grade 4 neutropenia;
- Grade \geq 3 neutropenia with fever > 38.3°C or > 38°C (> 100.9°F or > 100.4°F) for more than one hour;
- Grade \geq 3 thrombocytopenia with bleeding

Specific toxicity:

- Cytokine release syndrome (CRS); Grade 3 or 4. Furthermore, if a Grade >2 CRS occurs during the DLT period (Cycle 1), this also triggers the permanent discontinuation of all study dosing (birinapant AND pembrolizumab) with subsequent adequate care to treat the condition (see also sections 5.5.1 and 5.5.3).

If Day 8 of treatment is held due to toxicity then the event will be considered a DLT. A prolonged delay (> 2 weeks) in initiating Cycle 2 secondary to drug-related toxicity may be considered a DLT as judged by the SRC. Events related to disease progression, intercurrent illness, or concomitant medication will not constitute a DLT. Since patients are assessed for DLTs during the first cycle, dose modifications may not be performed. If a patient experiences a DLT that is deemed related to birinapant, the dose of birinapant may be restarted at a reduced level for Cycle 2 according to dose levels indicated in Table 2/[section 3](#) and the rules stated in [section 5.5](#), and the patient may remain on study.

The decisions to dose-escalate birinapant for each Dose Level are indicated in [Table 5](#) below.

Table 5 Escalation Decision Rules

Number of Patients with DLT at a Given Dose Level	Escalation-decision Rule

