Zero of 3 to 6	Enter 3 to 6 patients at the next dose level.
1 out of 3 to 6	Enter up to a total of 6 patients at this dose level. 
 • If 1 of these 3 to 6 patients experiences a DLT, proceed to the next dose level, if the next highest dose has not already been declared intolerable*. • If 1 of these 3 to 6 patients experiences a DLT and the next highest dose has already been declared intolerable, enroll a minimum of 6 patients at this dose level.
≥ 2 out of 3 to 6	Dose escalation will be stopped. This dose level may be declared the maximally administered dose (highest dose administered) and may be declared intolerable. Three additional patients may be entered at the next lowest dose level if only 3 patients were treated previously at that dose.

*Defined as ≥ 2 patients from 3-6 experiencing a DLT

Once the RP2D of birinapant combined with pembrolizumab is defined, additional patients with relapsed or refractory carcinoma will be enrolled in the dose-expansion phase of the study.

During the dose-expansion phase, an independent DMC will meet at least biannually to review the complete analysis of combined observed toxicities including emerging safety issues and reported SAEs. Such meetings may result in a reappraisal of the MTD and /or RP2D. In the event that dose de-escalation is to occur the same dose levels as indicated in Table 2 / [section 3.1.1](#) should be applied.

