Details regarding the investigational plan, patient selection criteria, dose administration, and schedule of assessments are given in the Clinical Study Protocol (CSP) ”BPT-201 v4.0/incl amendment 03”.

2. Study Objectives

2.1 *Study Objectives Dose Escalation Phase*

2.1.1 *Primary Objective*

To determine the safety and tolerability of the recommended phase 2 dose (RP2D) of birinapant when given in combination with pembrolizumab IV.

2.1.2 *Secondary Objective*

To assess preliminary efficacy of the combination of pembrolizumab and birinapant in patients with relapsed or refractory cancer by effects on tumor size as measured by imaging (CT or MRI) assessed by RECIST 1.1.

2.1.3 *Exploratory Objectives*

1. To assess preliminary efficacy of the combination of pembrolizumab and birinapant in patients with relapsed or refractory cancer by effects on tumor size as measured by imaging (CT or MRI) assessed by iRECIST.
2. To determine the pharmacodynamic markers of birinapant and of pembrolizumab when given in combination at the schedule and dose as defined by the protocol, to include but not to be limited to mechanism of action (inhibition of cIAP1), and of immune surveillance and activation.
3. To assess biomarkers that might predict for responders to the combination treatment and allow comparison to known potential predictive biomarkers of pembrolizumab response.
4. To evaluate birinapant pharmacokinetics in plasma when administered in combination with pembrolizumab.

2.2 *Study Objectives Dose Expansion Phase*

2.2.1 *Primary Objective*

The primary objective in each of the cohorts is as follows:

1. To determine whether the combination of pembrolizumab and birinapant has sufficient antitumor activity, as assessed by ORR, against colorectal cancer to warrant more extensive development.

2. To determine whether the combination of pembrolizumab and birinapant has sufficient antitumor activity, as assessed by ORR, against ovarian cancer to warrant more extensive development.
3. To determine whether the combination of pembrolizumab and birinapant has sufficient antitumor activity, as assessed by ORR, against cervical cancer to warrant more extensive development.
4. To determine the safety and tolerability of the RP2D of birinapant when given in combination with pembrolizumab to patients in the various solid tumors cohort

2.2.2 *Secondary Objectives*

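### The one-DLT escalation rule is worded inconsistently and, read literally, permits escalation after 1 DLT in only 3 patients

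*Protocol*

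**What the plan says.** Each dose level takes 3 to 6 evaluable patients (Protocol 3.1.1). The action after exactly one DLT is described in four places.

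- **Protocol 3.1.1 and SAP 3.1.1** use the same wording. If one of the 3 to 6 patients at a level "experiences a DLT, enrollment at the next dose level will proceed", unless the next dose is already intolerable. If it is, at least 6 patients must be enrolled at the current level.
- **Protocol 5.4, Table 5, and the synopsis table** begin the one-DLT row with "Enter up to a total of 6 patients at this dose level". The first sub-bullet then reads "If 1 of these 3 to 6 patients experiences a DLT, proceed to the next dose level", with the same proviso about the next dose. The second sub-bullet repeats the minimum of 6 when the next dose is intolerable.

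Section 5.4 makes Table 5 the operative source: "The decisions to dose-escalate birinapant for each Dose Level are indicated in" that table. Section 3.1.3 lists the SRC's options as escalating, stopping the study early, or "Alter the subsequent dose as per the dose escalation criteria presented in" Section 5.4. Expanding the current level is not listed. The section adds: "Further details on the SRC procedures are presented in the SRC-charter". The SAP does not reproduce the table. Its introduction states: "Details regarding the investigational plan, patient selection criteria, dose administration, and schedule of assessments are given in the Clinical Study Protocol".

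**The concern.** The range of 3 to 6 includes 3. Someone working from Protocol 3.1.1 or SAP 3.1.1 alone could open the next dose after 1 DLT in 3 patients. Someone working from the first line of the Table 5 row would more naturally fill the level to 6 first. A safety decision rule should not depend on which section is open.

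Patients treated at the next dose bear the consequence. If one DLT in three is followed directly by escalation, they receive a higher dose before it is known whether the current level would have met the protocol's own definition of intolerable, 2 or more DLTs in 3 to 6 patients.

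**Working it through.** **1. The plan's own figure.** The synopsis gives up to 24 patients for escalation. Levels 1 to 4 with 6 patients each give 4 × 6 = 24, so the figure is reproduced. The total already allows for filling every one of these levels to 6. The escalation phase has no power or error rate to reproduce, because Protocol 12.2 states that no formal calculation was made.

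**2. What the table row means.** The zero-DLT row already sends 3 to 6 patients to the next level. If 1 of 3 also escalated at once, the first line of the one-DLT row would do nothing. Zero and one DLT would lead to the same action whenever the next dose is not yet intolerable. Section 3.1.3 describes the final cohort as three plus three subjects. The row for 2 or more DLTs says "Three additional patients may be entered at the next lowest dose level if only 3 patients were treated previously at that dose". Both suggest that a conventional expansion was intended. Against this, a total given as *up to* 6 is a ceiling, and the first sub-bullet still accepts 3. The row favours expanding first without requiring it.

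**3. Chance of passing one level.** Let p be the true DLT probability, q = 1 − p, and n the number of patients first treated at the level (3, 4 or 5). The documents give no DLT rate for this combination, so the values of p are assumptions. SRC override is ignored.

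- Literal rule (0 or 1 DLT in n): qⁿ + n·p·qⁿ⁻¹
- Expand to 6 after one DLT, then escalate only if no more than 1 of 6: qⁿ + n·p·qⁿ⁻¹ × q⁶⁻ⁿ

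For n = 3 and p = 0.20, the literal rule gives 0.512 + 0.384 = 0.896. Expansion gives 0.512 + 0.384 × 0.512 = 0.709.

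| Starting n | p = 10%, literal vs expand | p = 20% | p = 33% (1/3) |
|---|---|---|---|
| 3 | 0.972 vs 0.906 | 0.896 vs 0.709 | 0.741 vs 0.428 |
| 4 | 0.948 vs 0.892 | 0.819 vs 0.672 | 0.593 vs 0.373 |
| 5 | 0.919 vs 0.886 | 0.737 vs 0.655 | 0.461 vs 0.351 |

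Across starting sizes the gap is 3 to 7 percentage points at 10% and 11 to 31 points at 33%.

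**4. What the extra patients reveal.** At p = 0.30, the chance of exactly one DLT in three is 3 × 0.3 × 0.49 = 0.441. Given that, three more patients show at least one further DLT with probability 1 − 0.7³ = 0.657, which makes the level intolerable by the protocol's definition.

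**5. Cost in patients.** The expected number added per level is (6 − n) × n·p·qⁿ⁻¹. At p = 10%, 20%, 33% and 40% this is:

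- n = 3: 0.73, 1.15, 1.33, 1.30
- n = 4: 0.58, 0.82, 0.79, 0.69
- n = 5: 0.33, 0.41, 0.33, 0.26

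**The case against.** The best defence is that this is loose drafting and not two opposed rules. All four places contain the same condition, one DLT in 3 to 6 and then proceed. In a single cell the authors used a ceiling (up to 6) in one line and a floor (a minimum of 6) in another, so optional expansion at the SRC's discretion is a coherent reading. That stands. A reader might infer that 3.1.1 and Table 5 flatly contradict each other. The documents do not support that, because the table repeats the 3.1.1 condition. But optional expansion with no criterion still leaves the action after 1 of 3 undefined.

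The SRC gate also stands. Protocol 3.1.1 requires the committee to decide whether the data support escalation, so moving up after 1 of 3 is permitted, not automatic. The charter, which is not available here, may say more. However, the option that refers the committee to Section 5.4 leads back to the ambiguous row.

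A reader might further infer that a poorly tested dose could become the RP2D. This wording does not support that inference: once the next dose proves intolerable, a one-DLT level must be filled to at least 6, and the SRC reviews the RP2D separately.

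Finally, the larger gaps in the table need high DLT rates. Protocol 1.6.1 reports birinapant up to 22 mg/m² weekly with chemotherapy and a monotherapy MTD of 47 mg/m². The lower rates may therefore be the relevant ones, although that experience was not with pembrolizumab.

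**Conclusion.** The one-DLT rule is stated inconsistently and, taken literally, allows escalation after 1 DLT in 3 patients. The governing table favours expanding first but does not settle the question, so correcting 3.1.1 alone would not be enough. The consequence is possible earlier exposure of patients at the next dose. No claim is made about the RP2D.

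Starting with 3 patients, the chance of passing a level is 97% against 91% at a 10% DLT rate, 90% against 71% at 20%, and 74% against 43% at 33%. These figures rest on assumed rates, independent patients, one level at a time and no SRC override. They compare always escalating after one DLT with always expanding first, so they show how much the two readings can differ and do not predict this trial. The point should be fixed because it concerns a safety rule and the correction is cheap.

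**What to change.** In Protocol 3.1.1, Table 5, the synopsis table and, for consistency, SAP 3.1.1, state one rule:

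*If 1 DLT occurs among fewer than 6 evaluable patients at a dose level, expand the level to 6 evaluable patients; escalate only if no more than 1 of the 6 has a DLT and the next highest dose has not been declared intolerable.*

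Then:

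- In Table 5 and the synopsis table, change *these 3 to 6* to *these 6* in the first (proceed) sub-bullet only. Leave the second sub-bullet unchanged; the same edit there would make it circular, asking for a minimum of 6 when 6 are already enrolled.
- Add *expand the current dose level to 6 evaluable patients* to the SRC options in Protocol 3.1.3.

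This changes wording in five places. It adds up to 3 evaluable patients at a level with one DLT, on average about 0.3 to 1.3 depending on starting size, at assumed rates of 10% to 40%. That stays within 3 to 6 per level and 24 in total. Replacing non-evaluable patients under Protocol 12.2 could take enrolment above 24, as it already can. If the sponsor meant expansion to be optional, this is a small design change and should be presented as one.
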